3.2.2. Maximum Tolerated Dose

The BOIN design will be employed to find the MTD of continuous RP-6306 (Module 1a) and, if necessary, intermittent RP-6306 (Module 1b) in combination with FOLFIRI. The target toxicity rate is 25%. DLTs occurring within the first 28 days (2 cycles) will be used to direct MTD finding.

The BOIN design uses the following criteria, optimized to minimize the probability of incorrect dose assignment, to guide dose escalation/de-escalation:

- If the observed DLT rate at the current dose is ≤0.197 (<20%), escalate the dose to 1 of the 2 next higher dose levels (ie, 1 level increase of RP-6306 or 1 level increase of FOLFIRI).
- If the observed DLT rate at the current dose is ≥ 0.298 ($\ge 30\%$), de-escalate the dose to 1 of the 2 next lower dose levels (ie, 1 level decrease of RP-6306 or 1 level decrease of FOLFIRI).
- Otherwise, stay at the current dose.

 Table 2:
 Dose Escalation/De-Escalation Rules for the BOIN Design

Action	Number of Evaluable Patients at Current Dose Level											
Action	1	2	3	4	5	6	7	8	9	10	11	12
\uparrow if number of DLT \leq	0	0	0	0	0	1	1	1	1	1	2	2

Stay current dose if number of DLT =	NA	NA	NA	1	1	NA	2	2	2	2	3	3
\downarrow if number of DLT \geq	1	1	1	2	2	2	3	3	3	3	4	4
Elim if number of DLT ≥	NA	NA	3	3	3	4	4	4	5	5	6	6

BOIN = Bayesian optimal interval; \uparrow = increase, \downarrow = decrease, DLT = dose-limiting toxicity, Elim=eliminate, NA = not applicable, dose cannot be eliminated until at least 3 patients have been treated

Note: Number of DLT is the number of patients with at least 1 DLT. When none of the actions (ie, escalate, de-escalate or eliminate) is triggered, stay at the current dose for treating the next cohort of patients.

Dose finding starts at Dose Level 1. The steps to implement the BOIN design are described as follows:

- 1. Patients in the first cohort are treated at Dose Level 1. Dose decisions will depend on 2 or more evaluable patients completing the first 2 14-day treatment cycles.
- 2. To assign a dose to the next cohort of patients, conduct dose escalation/de-escalation according to the rule displayed in Table 2. When using Table B, please note the following:
 - a. "Eliminate" means eliminate the current and higher doses from the trial to prevent treating any future patients at these doses because they are overly toxic.
 - b. When we eliminate a dose, automatically de-escalate the dose to the next lower level. When the lowest dose is eliminated, stop the trial for safety. In this case, no dose should be selected as the MTD.
 - c. If none of the actions (i.e., escalation, de-escalation or elimination) is triggered, treat the new patients at the current dose.
 - d. If the current dose is the lowest dose and the rule indicates dose de-escalation, treat the new patients at the lowest dose unless the number of DLTs reaches the elimination boundary, at which point terminate the trial for safety.
 - e. If the current dose is the highest dose and the rule indicates dose escalation, treat the new patients at the highest dose.
- 2. To assign a dose to the next cohort of patients, conduct dose escalation/de-escalation according to the rule displayed in Table 2. When using Table 2, please note the following:
 - a. "Eliminate" means eliminate the current and higher doses from the trial to prevent treating any future patients at these doses because they are overly toxic.
 - b. When we eliminate a dose, automatically de-escalate the dose to the next lower level. When the lowest dose is eliminated, stop the trial for safety. In this case, no dose should be selected as the MTD.
 - c. If none of the actions (i.e., escalation, de-escalation or elimination) is triggered, treat the new patients at the current dose.

- d. If the current dose is the lowest dose and the rule indicates dose de-escalation, treat the new patients at the lowest dose unless the number of DLTs reaches the elimination boundary, at which point terminate the trial for safety.
- e. If the current dose is the highest dose and the rule indicates dose escalation, treat the new patients at the highest dose.
- 3. Repeat Step 2 until the maximum sample size of 36 evaluable patients is reached for the corresponding module or stop the trial early if the number of evaluable patients treated at the current dose \geq 9 and the decision according to Table B is to stay at the current dose.

After the study is completed, results from all DLT evaluable patients, including the relevant backfill cohorts, will be included to assess the MTD. The dose for which the isotonic estimate of the toxicity rate is closest to and no higher than 30% will be selected as the MTD. This computation can be implemented by the shiny app "BOIN" available at http://www.trialdesign.org. The RP2D for RP 6306 and FOLFIRI will be based on discussion between the Investigators and the Sponsor and will be the dose that at or lower than the MTD based on the totality of the safety, PK, pharmacodynamics, and preliminary efficacy.

3.3. Sample Size Considerations

The maximum total sample size for this study is 104 patients. The maximum sample size for the Dose Finding Phase is 36 evaluable patients per module (72 patients total if an intermittent dosing schedule is initiated). The population used for determination of DLTs will consist of patients who have met the minimum safety evaluation requirements of the study and/or who have experienced a DLT at any time during the initial 28 days (2 cycles) of the study (Section 11.1 of the protocol). Minimum safety requirements will be met if, during the first 2 cycles of treatment the patient receives at least 75% of planned total doses of RP-6306 for the evaluated schedule, 100% of planned doses of FOLFIRI, completes all required safety evaluations per Schedule of Assessments (Section 12.1 of the protocol), and are observed at least until Day 28 since the first dose of study treatment. Thus, the possible total number per module may be slightly higher at 40 patients (approximately +10%; 80 total patients). Depending on the toxicity profile of the combination and the number of dose levels required to establish the MTD/RP2D, the actual study sample size may vary. Approximately, an additional 24 patients will be planned for backfill cohorts.

4. ANALYSIS POPULATIONS

4.1. DLT Evaluable Population

DLT Evaluable Population will consist of patients who have met the minimum safety evaluation requirements of the study and/or who experience a DLT at any time during the first two cycles (28 days) of the study. Minimum safety requirements will be met if, during the first 2 cycles of treatment, the patient receives at least 75% of planned total doses of RP-6306 for the evaluated schedule, 100% of planned doses of FOLFIRI, completes all required safety evaluations per the Schedule of Assessments (refer to Section 12.1 of the protocol), and is observed at least until Day 28 since the first dose of study treatment.

4.2. Efficacy Population

The Efficacy Population, used for the assessment of efficacy, will consist of all patients who receive at least 1 dose of study treatment and had at least 1 post-baseline tumor assessment based on RECIST v1.1 or without post-baseline tumor assessment but discontinued the treatment due to clinical progression or death prior to any post-baseline tumor assessment, and have local confirmation of their genomic alterations.

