 patient prior to the performance of any study-specific procedures, sampling, or analyses.
 Patients with impaired decision-making capacity must have a close caregiver or legally
 authorized representative present.
- 2. Males or females \geq 18 years old at the time of signature of the ICF.
- 3. ECOG performance status of 0 or 1.
- 4. All patients must have locally advanced or metastatic CRC, GI, or esophageal cancer(s) and radiographic evidence of progressing disease or any solid tumor with eligible molecular alterations (see criterion 6) that in the opinion of the Investigator are suitable for therapy with FOLFIRI regimen. Patients will be eligible if they have received no more than 3 prior treatment regimens, excluding adjuvant treatment. If the Investigator considers the patient a

candidate for FOLFIRI as initial treatment of newly diagnosed, metastatic, or advanced disease, the patient is eligible.

- 5. A recent archival tumor tissue sample must be shipped to the Sponsor's central laboratory. Patients who do not have archival tumor tissue that meets the specifications detailed in the Laboratory Manual should undergo a fresh tumor biopsy prior to treatment if it is considered safe to perform. If adequate archived tumor tissue is not available and/or a fresh biopsy cannot be safely performed, the patient may still be eligible with prior Sponsor approval.
- 6. All patient's tumors must have evidence of at least one of the following as reported by a local CLIA-certified or equivalent (ex-United States [US]) laboratory:
 - a. CCNE1 amplification (nonequivocal) as determined by tumor or plasma NGS or FISH
 - b. FBXW7 deleterious mutations (eg, hotspot, truncating, splice site, frameshift) identified by either tumor or plasma NGS test
 - c. Other genetic alterations with mechanistic rationale agreed upon by the Sponsor and the Investigator, determined by a tumor NGS test

Note: For all patients, an anonymized/redacted Molecular Pathology or other report(s) describing CCNE1, FBXW7 or other genomic alterations should be submitted to the Sponsor or designee during Screening to confirm eligibility.

- 7. Measurable disease as per RECIST v1.1.
- 8. Ability to comply with the protocol and study procedures detailed in the Schedule of Assessments.
- 9. Acceptable organ function at Screening, as evidenced by the following laboratory data:

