The maximum total sample size for this study is 104 patients. The maximum sample size for the Dose Finding Phase is 36 evaluable patients per Module (72 patients total if an intermittent dosing schedule is initiated). The population used for determination of DLTs will consist of patients who have met the minimum safety evaluation requirements of the study, and/or who have experienced a DLT at any time during the initial 28 days (2 cycles) of the study. Minimum safety requirements will be met if, during the first 2 cycles of treatment, the patient receives at least 75% of planned total doses of RP-6306 for the evaluated schedule, 100% of planned doses of FOLFIRI, completes all required safety evaluations per Schedule of Assessments, and are observed at least until Day 28 since the first dose of study treatment. Thus, the possible total number per Module may be slightly higher at 40 patients (approximately +10%, 80 total patients). Depending on the toxicity profile of the combination and the number of dose levels required to establish the MTD/RP2D, the actual study sample size may vary. Approximately an additional 24 patients will be planned for backfill cohorts.

Analysis Populations

The following analysis populations will be used:

[figure not shown]
- DLT Evaluable Population for dose decisions will be as defined above.
- The Safety Population, used for the assessment of overall safety and tolerability, will consist of all patients who receive at least one dose of study treatment. Patients will be assessed for safety based on the dose level in which they were enrolled.
- The Efficacy Population, used for the assessment of efficacy, will consist of all patients who have measurable disease, are exposed to at least one dose of study treatment, and have local confirmation of their genomic alterations.
- The PK Population, used for the assessment of PK endpoints, will consist of all
 patients who have sufficient RP-6306, irinotecan, or SN-38 plasma concentration data
 recorded to derive PK endpoints.

Efficacy Analysis:

Approximately 24 additional patients will be enrolled in backfill cohorts ($N \le 8$ per cohort) to further evaluate the safety/tolerability profile in specific patient populations (eg, specific cancer types or patients that are high-risk for toxicities),

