5. DATA AND ANALYSIS CONSIDERATIONS

5.1. General Principles

All demography and safety data will be presented by the safety population, except for the DLT reporting which will be based on the DLT evaluable population. Assessment of anti-tumor activity will be based on the Efficacy Population and PK data will be presented by the PK Population.

Most of the analyses will be descriptive in nature. Unless stated otherwise, continuous variables will be summarized using descriptive statistics (number of patients, mean, standard deviation, median, lower and upper quartile, minimum and maximum values) and the number and percentage of patients will be used for categorical variables. In general, missing data will be considered as missing and will not be imputed. Unless stated otherwise, percentages will be calculated out of the number of patients in the relevant analysis population.

Baseline will be the last assessment of the variable under consideration prior to first dose of RP-6306.

Unless stated otherwise, safety and efficacy data will be presented by assigned dose/schedule.

After determination of RP2D dose(s), safety and efficacy data may also be summarized by grouping dose levels based on RP2D and clinical relevance.

All DLT rates will be summarized by the assigned initial dose levels.

Summary statistics will be presented to the following degree of precision unless otherwise specified:

	Degree of Precision
Mean, Geometric mean, Median, Quartiles, Confidence limit boundaries	One more decimal digit than the raw data.
Standard deviation, Standard error	Up to 2 more than the raw data
Minimum, Maximum	The same decimal digit as the raw data.
Percentage	One decimal place. A percentage of 100% will be reported as 100%. Percentages of zero will be reported as 0.

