8. EFFICACY DATA

The efficacy analysis will be summarized by dose combination. Data from the backfill cohorts will be pooled with patients from the Dose Finding Phase that were treated at the RP2D (a minimum of 6 patients are expected to be treated at the RP2D during dose finding) when applicable.

Efficacy data will be summarized using the Efficacy Population.

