8.1.2. Objective Response Rate (ORR)

Objective Response Rate (ORR) is defined as the proportion of patients with a confirmed response of CR or PR (i.e., 2 visit responses of either CR or PR at least 4 weeks apart) according to RECIST v1.1 criteria. This analysis will be limited to patients with measurable disease.

• Response will be assessed based on all evaluable assessments up to and including progression per RECIST v1.1. Responses occurring following subsequent anti-cancer therapy will be excluded from the assessment of ORR but will be included in the listing.

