8.1.3. Best Overall Response Rate

Best Overall Response Rate is defined as the proportion of patients with confirmed or unconfirmed response of CR or PR based on best overall response by investigators across all visits. Unconfirmed CR or PR will be defined as those patients with CR or PR only reported once in overall tumor assessment form by the Investigators according to RECIST 1.1.

Note that the unconfirmed CR or PR (assessed by investigator) is added as a response criterion in addition to protocol defined confirmed CR or PR, to identify signal of anti-tumor activity for the treatment.

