8.2. Efficacy Analysis Methods

For overall response rate, ORR, and CBR, the number and percentage of patients along with an exact binomial 95% confidence interval (CI), using the Clopper-Pearson method, will be presented.

In general, summary of all efficacy endpoints will be provided by dose level separately for Module 1a and 1b patients.

The assessment of tumor efficacy will be based on the measurements recorded by the investigator.

A summary of the best objective response will be presented which will include the number and percentage of patients with a best response of CR, PR, SD, PD and NE.

Time-to-event endpoints (PFS) will be analyzed using the KM method and results will be summarized by the 25th, 50th and 75th percentiles, if estimable, with associated 2-sided 95% CIs. KM plots will be provided. For PFS, the number (%) of patients with an event and the number (%) of patients censored will also be presented. The rate of PFS at 16 weeks and 24 weeks will be derived from the corresponding Kaplan-Meier curves. The KM analyses for DOR may be replaced by descriptive summary of median, and quartiles with individual listing for responders if total confirmed responders are few and less than 5 patients.

Maximum reduction in tumor size will be summarized by n, mean, standard deviation, median, 25th quartile and 75th quartile, minimum and maximum. The spider plots displaying change in tumor size over time for each patient will also be provided for each module and dose/schedule group as described above.

In addition, waterfall plots showing the best percentage change from baseline (largest decrease or smallest increase in the absence of a decrease) in the sum of the TL sizes will be produced for each module by dose/schedule group indicating each patient' best objective response.

Swimmer plots will be produced for each module and dose/schedule group to show the duration of study treatment per patient with indicators for timing of response, progression or death, where applicable.

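### SAP 4.2 adds a post-baseline scan condition to the protocol's Efficacy Population, which can only leave ORR unchanged or raise it; SAP 8.1.1 and 8.1.7 also give conflicting rules for best tumor change

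*SAP*

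**What the plan says.** **Efficacy Population.** In the protocol synopsis (Analysis Populations) this set "will consist of all patients who have measurable disease, are exposed to at least one dose of study treatment"; a locally confirmed genomic alteration is the third condition. It has no scan condition. SAP 4.2 keeps the dose and genomic conditions and drops measurable disease. It requires that the patient "had at least 1 post-baseline tumor assessment based on RECIST v1.1 or without post-baseline tumor assessment but discontinued the treatment due to clinical progression"; the waiver also covers patients who died before any such assessment.

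SAP 8 states: "Efficacy data will be summarized using the Efficacy Population". SAP 5.1 adds that, unless stated otherwise, "percentages will be calculated out of the number of patients in the relevant analysis population". For ORR, SAP 8.1.2 says: "This analysis will be limited to patients with measurable disease". Inclusion criterion 7 in the synopsis is "Measurable disease as per RECIST v1.1". Under SAP 8.2 a "summary of all efficacy endpoints will be provided by dose level separately for Module 1a and 1b patients".

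**Best percent change in tumor size.** SAP 2.2.2 and 8.1.1 take the largest decrease (or smallest increase) in the target-lesion sum from assessments before progression. SAP 8.1.7 takes it from assessments through progression, with the progression assessment included. The waterfall-plot text in SAP 8.2 names neither rule.

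**The concern.** The same population name carries two definitions, and the SAP does not mark the change. Elsewhere it does: SAP 8.1.3 says that unconfirmed response "is added as a response criterion in addition to protocol defined confirmed CR or PR". SAP 4.2 has no such note. SAP 6.1 says that there is no per-protocol population and that deviations do not lead to exclusion, yet 4.2 removes a treated patient whose only failing is missed scans. The PFS rules in SAP 8.1.8 have a row for patients with no post-baseline assessment and no death, so the SAP expects some unscanned patients.

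For ORR the effect runs one way, and with small groups by dose level a single removed patient is visible. For tumor change, two programmers who each follow the SAP could produce different summaries and waterfall plots from the same data.

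**Working it through.** **Part 1: direction for ORR**

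The documents state no ORR target or precision, so there is no planned figure to reproduce. The check compares the two sets.

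- n = patients in the protocol set; r = confirmed responders.
- k = patients in that set with no post-baseline scan who did not stop for clinical progression or death.
- SAP 8.1.2 limits ORR to measurable disease, so dropping that condition in 4.2 does not affect ORR. The scan condition is the only remaining difference.
- A confirmed response needs two responses at least 4 weeks apart (SAP 8.1.2), so none of the k patients is a responder.

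Protocol ORR = r/n. SAP ORR = r/(n − k). The difference is rk/[n(n − k)], which is never negative and is zero only if r = 0 or k = 0.

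**Size, with assumed r and k** (Clopper-Pearson 95% limits, the method in SAP 8.2)

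- n = 6, the minimum expected at the RP2D during dose finding (SAP 8). With r = 2 and k = 1: 2/6 = 33.3% (4.3 to 77.7) becomes 2/5 = 40.0% (5.3 to 85.3). Difference: 2 × 1/(6 × 5) = 6.7 points.
- n = 30 = 6 + 24, if all of the roughly 24 backfill patients were treated at the RP2D, which the documents do not say. With r = 6 and k = 3: 6/30 = 20.0% (7.7 to 38.6) becomes 6/27 = 22.2% (8.6 to 42.3). Difference: 6 × 3/(30 × 27) = 2.2 points.

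Both shifts are small against their intervals.

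**Part 2: best percent change**

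SAP 8.1.7 gives (visit sum − baseline sum)/baseline sum × 100. Take an invented patient with a baseline sum of 100 mm, a first scan of 90 mm (stable), and a second scan of 75 mm with a new lesion (progression).

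- First scan: (90 − 100)/100 = −10%.
- Second scan: (75 − 100)/100 = −25%.
- SAP 2.2.2 and 8.1.1 use only the first scan: best change −10%.
- SAP 8.1.7 uses both: best change −25%.

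Now take a patient whose first scan is 130 mm (progression). SAP 8.1.7 gives (130 − 100)/100 = +30%. SAP 8.1.1 is unclear. Its main sentence leaves no scan before progression to use, but its exclusion bullet removes only patients with no evaluable post-treatment target-lesion assessment, and this patient has one.

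**The case against.** The protocol leaves detailed methodology to the SAP, and a response-evaluable set is a recognisable choice. The waiver in 4.2 keeps early clinical progressions and deaths, the unscanned patients most likely to be treatment failures. The endpoints are secondary and descriptive, no ORR threshold selects the RP2D, and SAP 6 will show the count in each population by dose. All of this stands and limits the weight of the point. It does not remove the unmarked difference between two definitions with one name.

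A second objection changes the remedy. The SAP reports at a data cutoff at which patients may still be on treatment (SAP 6 and 7.2), and the first scan is due at 6 weeks ± 7 days (protocol synopsis, Efficacy). Counting a recently dosed patient as a non-responder would push ORR down for no good reason, so a blanket rule would be wrong.

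Some stronger readings are tempting but not supported:

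- *Dropping measurable disease distorts the results.* Criterion 7 requires it at entry and SAP 8.1.2 restores it for ORR, so only eligibility deviations could matter.
- *Patients who stop for toxicity disappear.* The synopsis asks for scans to continue after such stops, until progression or new anticancer treatment, so most should stay in.
- *Every response endpoint is pushed upward.* The one-way result is shown for ORR only. Best overall response rate has no stated measurable-disease limit, and CBR has a 16-week on-treatment route that does not itself require a response.
- *SAP 8.1.1 excludes patients whose first scan is progression.* Its text is unclear on this and does not settle it.

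**Conclusion.** Both conflicts are in the text and should be resolved before database lock.

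For ORR, the SAP set gives a rate equal to or higher than the protocol set. The patients concerned are those treated but never scanned for reasons such as consent withdrawal, new anticancer therapy or missed scans. The direction follows from SAP 4.2 together with 8.1.2. The size cannot be derived, because the documents give no rate of unscanned patients; under the assumed counts it is 2.2 to 6.7 points, well inside the intervals. A reader might infer that the reported ORR will be materially inflated or that the RP2D choice is compromised. The documents support neither.

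For best percent change, the two rules give different values for the same patient whenever target lesions are at their smallest at a progression caused by new or non-target lesions.

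Two limits apply. The comparison is with the protocol synopsis, since the protocol body was not supplied. The SAP cites protocol Version 3.0, and the version supplied cannot be confirmed as that one.

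**What to change.** **Population.**

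- In SAP 4.2, restore the protocol definition as the Efficacy Population for all efficacy endpoints.
- PFS keeps the censoring rules in SAP 8.1.8. DOR stays limited to confirmed responders. Tumor change is limited to patients with an evaluable post-baseline target-lesion assessment.
- For ORR and best overall response rate, count patients with no post-baseline scan as NE and non-responders, and word the categories in SAP 8.1.6 to match.
- The exception is a patient still on treatment at data cutoff whose first scheduled scan is not yet due. Leave such patients out of the response denominator and footnote their number.
- Keep the present SAP set as a labelled response-evaluable sensitivity analysis.

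**Tumor change.** Use one rule in SAP 2.2.2, 8.1.1, 8.1.7 and the waterfall text of 8.2: all values through the progression visit, with that visit included. This also settles the patient whose first scan is progression. Apply it by visit, because SAP 8.1.8 allows lesion assessments on different dates and takes the earliest triggering date as progression; a date-based rule could exclude a target sum from the same visit.

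**Cost.** Wording changes in the SAP, one extra table, and a reported ORR that may be slightly lower.
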